5.3 Lifestyle Considerations

Enrolled subjects should practice good skin hygiene during the screening and treatment periods by limiting bathing/showers (preferably once daily with tepid water and of short duration) and by using mild cleansers and non-sensitizing emollients. Dietary and activity-related restrictions are not required for this study other than limiting alcohol usage. In general subjects should be instructed that if they experience dizziness, they should avoid potentially hazardous tasks such as driving or operating machinery.

5.3.1 Use of Cleanser, Moisturizer, and Sunscreen During the Study

Subjects may use their own mild cleanser up to twice daily and bland emollient cream therapy once daily. Site staff should review and confirm the cleanser and emollient are acceptable for use (eg, not mediated) at Screening. Bleach baths are not permitted during the study.

Subjects may apply the approved bland emollient cream therapy to non-involved skin once daily at least 15 minutes after application of investigational product. Emollients should not be used in the 24 hours prior to the Baseline Visit, Day 15, or Day 29.

Sun exposure of treatment areas should be avoided. If the location of the treatment sites makes avoidance of sun exposure not feasible, protective clothing and application of an approved

sunscreen with a sun protection factor (SPF) of at least 15 should be used and should be applied at least 15 minutes after application of study interventions.

Throughout the duration of the study, subjects may use their preferred shampoo and may apply makeup to the face. Cosmetics should be applied at least 15 minutes after study drug application. Makeup should not be used in the 24 hours prior to the Baseline Visit and Day 29 Visit.

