If severe local application site AEs or scores of 3 on two or more tolerability subscores arise with BID dosing, treatment will be withheld to the affected area. When the local AE(s) has resolved or tolerability score returns to baseline, subjects may restart application to the affected area once daily. See [Section 6.2](#) of protocol.

Pharmacokinetics: Trough levels on Days 15, 29.

Other Assessments:

Photography of representative lesions will be taken at baseline, Day 15, and Day 29. The same areas will be photographed throughout the study under the same conditions.

Statistical Methods:

The sample size is based on a clinical rather than statistical rationale. Approximately 60 subjects are planned to be enrolled and randomized, considering a potential 15% dropout rate, to yield approximately 50 subjects completing the study. Statistical analyses will be exploratory to assess the drug's activity and potential for further study.

All randomized subjects who receive at least 1 application of the study treatment will be included in the Safety Analysis Set (SS). All randomized subjects who receive at least 1 application of the study treatment and have 1 post-baseline efficacy assessment will be included in the Efficacy Analysis Set (ES). All subjects in ES without major protocol deviations will be included in the Per Protocol Efficacy Analysis Set (PPES).

The primary efficacy endpoint (percent change in EASI total score) will be analyzed using a mixed model for repeated measures (MMRM). The model will include fixed effects for study treatment (TER-101 [2.75% w/w] ointment or vehicle), visit (Day 15, Day 29), and treatment-

by-visit interaction with visit as the repeating factor, subject as a random effect, and baseline score as a covariate. The treatment p-value (TER-101 [2.75% w/w] ointment vs. vehicle), treatment difference, and 95% confidence limits from the model will be presented for the percent change in EASI from baseline at Day 29. Sensitivity analyses will include analysis of covariance (ANCOVA) at each timepoint. The impact of dropouts and missing data on results for the primary endpoint will be explored using the last value carried forward (LOCF) and multiple imputation methods, as appropriate.

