4 STUDY DESIGN

4.1 Overall Design

This is a Phase 2a, randomized, double-blind, vehicle-controlled study assessing efficacy and safety, and local tolerability of TER-101 (2.75% w/w) ointment vs. its ointment vehicle topically twice daily in adolescent and adult subjects (age 12 - 65) subjects with mild to moderate AD.

Subjects will be randomized 1:1 to receive either TER-101 (2.75% w/w) ointment or vehicle. Both the subject and the investigator will be blinded to the treatment assignments.

Approximately 60 adolescent and adult subjects (age 12 – 65) are planned to be enrolled across approximately 12 clinical research sites in the United States. Institutional Review Board (IRB) approval will be obtained for each clinical research site prior to recruiting any subjects at the site.

The study will include up to a 35-day screening period prior to enrollment/baseline visit and a 28-day active treatment period. Subjects will apply assigned treatment to all areas affected by AD at baseline twice daily throughout the treatment period. If the subject develops new areas of AD, those areas will also be treated. Treatment areas will exclude the scalp, nose, mouth and eyes. Subjects may use bland emollients on non-affected body sites once daily. Rescue medications are not permitted.

Efficacy assessments will include the EASI, Investigator Global Assessment (IGA), Worst Itch Numeric Rating Scale (WI-NRS), and Total Body Surface Area (TBSA) affected. Safety and tolerability assessments will include reported adverse events (AEs), clinical laboratories, physical examinations, ECGs, and vital signs as well as a separate tolerability assessment for treated areas. Systemic exposure will be determined by measuring trough TER-101 levels on Day 15 and Day 29/End of Trial (EOT). Photographs of representative areas of AD will be obtained at baseline, Day 15, and Day 29/EOT. The study procedures and visit timelines are described in the Schedule of Activities (SoA; [Table 1](#)). An overview of the study design is presented in [Figure 1](#).

If there are no safety concerns identified in the study, but additional subjects are needed to reach 50 subjects completing the study for efficacy, then additional subjects may be enrolled and randomized.

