4.1.3 Treatment Period (Day 1 to Day 29)

Subjects will continue to administer study agent twice daily, morning and evening, from Day 1 to Day 28 to all areas identified at the Baseline Visit and record each application in the e-diary. Study drug will be applied as a thin film to all involved areas twice daily, with at least 8 hours between applications. New areas that develop during the trial will be treated with study drug. Study drug will not be applied to the scalp, mouth, inside the nose, or eyes.

Subjects will be contacted by phone or video on Day 8 to assess for AEs, adherence with study agent application and prohibited medication use, and WI-NRS and e-diary completion. Compliance with study agent application will be emphasized.

Subjects will be present for in person visits on Day 15 and Day 29 when efficacy will be assessed using IGA, EASI, and TBSA. Safety assessments, including AEs, vital signs, urine pregnancy test, clinical laboratory tests, ECG, and local tolerability assessments will be conducted as per the SoA. The scores for WI-NRS will be reviewed. Adherence to study agent application will be confirmed by collecting and reviewing the e-diary at each visit and obtaining weight of the medication tubes at in person visits on Day 15 and Day 29/EOT. Standardized photographs of the same areas photographed at baseline will be obtained as per the SoA. If necessary, study procedures and visits may be modified in response to needs related to eg, coronavirus disease 2019 (COVID-19) (see [Section 8](#) and SoA [[Table 1](#)]).

Regardless if the lesions are decreased in area or resolved prior to the scheduled end of treatment (Day 29), the subject should continue to apply study drug twice daily for the entire treatment

period. New lesions that arise post-baseline will also be treated. Subjects will be instructed to bring all investigational product (used and unused tubes) to study visits on Day 15 and Day 29.

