8.2.1 Investigator Global Assessment

The IGA is a 5-point scale that provides a global clinical assessment of overall AD severity based on an ordinal scale. The assessment is static, meaning that the evaluation is done without reference to any other time point.

0 = Clear: minor residual hypo/hyperpigmentation; no erythema or induration/papulation; no oozing/crusting.

1 = Almost clear: trace faint pink erythema, with barely perceptible induration/papulation and no oozing/crusting.

2 = Mild: faint pink erythema with mild induration/papulation and no oozing/crusting.

3 = Moderate: pink-red erythema with moderate induration/papulation with or without oozing/crusting.

4 = Severe: deep or bright red erythema with severe induration/papulation and with oozing/crusting.

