8.2.2 Eczema Area Severity Index

The EASI is a scoring system that measures 4 clinical signs, the extent of BSA involved, over 4 separate areas (head/neck, trunk, upper extremities, and lower extremities). Total EASI scores range from 0 to 72.

The 4 clinical signs are:

- Erythema
- Induration/papulation
- Excoriation
- Lichenification

And each feature is graded for each region on a 4-point severity scale of 0 to 3, as below, with:

- 0 = absent
- 1 = mild
- 2 = moderate
- 3 = severe

The investigator or qualified assessor will enter the value for erythema, induration/papulation, excoriation and lichenification and extent of BSA for each region on the eCRF page. The EASI score will be calculated by the sponsor/designee. See Appendix 6 ([Section 10.6](#)).

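### Makeup is barred before Baseline and Day 29 but not before Day 15, which adds avoidable measurement error to the Day 15 facial scores

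*Protocol*

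**What the plan says.** Protocol Section 5.3.1 gives a general permission: "Throughout the duration of the study, subjects may use their preferred shampoo and may apply makeup to the face". It then limits it: "Makeup should not be used in the 24 hours prior to the Baseline Visit and Day 29 Visit". For emollients, the same section says: "Emollients should not be used in the 24 hours prior to the Baseline Visit, Day 15, or Day 29". Neither the protocol nor the SAP extends the makeup limit to Day 15 or explains why the two rules differ.

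Day 15 is a scored visit. Protocol Section 4.1.3 states: "Subjects will be present for in person visits on Day 15 and Day 29 when efficacy will be assessed using IGA, EASI, and TBSA". The Schedule of Activities adds local tolerability and photography on that day.

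On the treated area, Section 4.1 states: "Treatment areas will exclude the scalp, nose, mouth and eyes". The rest of the face is not excluded, and Section 5.3.1 tells subjects how long to wait after study drug before putting on cosmetics. Head/neck is one of the four EASI regions (Protocol 8.2.2 and Appendix 6). Redness also enters the IGA, where grade 2, for example, reads "2 = Mild: faint pink erythema with mild induration/papulation and no oozing/crusting".

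**The concern.** Baseline is scored on a face without makeup, while Day 15 may be scored over it. Makeup conceals colour, so a subject with facial disease who wears it can receive a lower erythema grade at Day 15 with no change in the skin. By Day 29 the makeup is off again, and the same subject appears to worsen.

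The Day 15 results at stake are percent and absolute change in EASI, EASI by region (including head), EASI-50 and EASI-75, and IGA. Facial application-site erythema could also go unrecorded at Day 15. That is the only scheduled tolerability assessment between the 15-minute check after the first dose and Day 29, and tolerability scores feed the dose-modification rule in Protocol Section 6.2.

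**Working it through.** No sample size or power figure bears on this point. The check uses the EASI scoring table in Protocol Appendix 6, repeated in SAP Section 2.4.2.1.

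**Inputs.** From the documents: head/neck multiplier 0.1; area score 0 to 6; four signs graded 0 to 3; baseline EASI of at least 5 (inclusion criterion 7); 60 subjects planned with 15% dropout (Protocol 9.2). Assumed: an alternative baseline EASI of 10, the number of grades hidden, and the share of subjects affected.

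**1. The formula reproduces the stated range.** Region score = multiplier x area score x sum of the four sign grades. The maximum is (0.1 + 0.3 + 0.2 + 0.4) x 6 x 12 = 72, as stated. Head/neck accounts for 0.1 x 6 x 12 = 7.2 of this, or 10%.

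**2. Effect on one subject's total EASI.** Hiding d erythema grades at head/neck area score A lowers the total by 0.1 x A x d.

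| A | d | EASI points | Baseline 5 | Baseline 10 |
|---|---|---|---|---|
| 1 | 1 | 0.1 | 2% | 1% |
| 2 | 1 | 0.2 | 4% | 2% |
| 2 | 2 | 0.4 | 8% | 4% |
| 3 | 1 | 0.3 | 6% | 3% |
| 6 | 1 | 0.6 | 12% | 6% |

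The extreme, grade 3 fully hidden at area score 6, is 0.1 x 6 x 3 = 1.8 points.

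**3. A responder can change.** Take baseline 5 and a true Day 15 score of 2.7: (5 - 2.7)/5 = 46%, not an EASI-50 responder. One hidden grade at area score 3 gives 2.7 - 0.3 = 2.4, and (5 - 2.4)/5 = 52%, a responder.

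**4. Head-region EASI is more exposed.** SAP Section 3.6.1 analyses percent change by region. With the area score unchanged, the multiplier and area score cancel, so the error is d divided by the baseline sum of sign grades. For a sum of 6, one hidden grade gives 1/6 = 17 percentage points and two give 2/6 = 33.

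**5. Arm means at Day 15.** If 10 to 20% of subjects are affected by 4 to 8 points each, the arm mean shifts by 0.10 x 4 = 0.4 to 0.20 x 8 = 1.6 percentage points.

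**6. Difference between arms.** With equal masking in both arms the expected shift in the difference is about 0. If masking differed by chance by 10 to 20 percentage points, with 2 to 12 points per masked subject, the shift would be 0.10 x 2 = 0.2 to 0.20 x 12 = 2.4 percentage points, in either direction.

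**7. Primary endpoint.** Baseline and Day 29 are both covered by the makeup limit. The primary MMRM has visit and treatment-by-visit terms, so a uniform Day 15 shift is absorbed there and does not move the Day 29 contrast. Day 15 values matter mainly where Day 29 is missing: the MMRM then draws on Day 15, and the LOCF analysis carries it forward. The planned dropout is 0.15 x 60 = 9 subjects. Even if all 9 have a Day 15 score, the shift in an LOCF arm mean, on the assumptions in step 5, is 0.15 x 0.4 = 0.06 to 0.15 x 1.6 = 0.24 percentage points.

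**The case against.** The difference may be deliberate. Baseline and Day 29 define the primary endpoint, and the Synopsis singles out the same two visits when it recommends a consistent evaluator. Tighter control there and less burden at the interim visit is a defensible choice. The emollient sentence suggests an oversight but does not prove one.

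The effect is also limited. Head/neck carries the smallest EASI weight. Erythema is one of four signs, and the other three do not rest on colour. An assessor who sees the subject in person may not be fully misled. Tolerability erythema is averaged over all application sites (Appendix 7), so makeup hides only the facial part. For photographs the Synopsis already requires: "The same areas will be photographed throughout the study under the same conditions". A facial photograph over makeup at Day 15 would breach that. The study is exploratory. That the face is treated is an inference from the exclusion list and the cosmetics instruction, though a safe one.

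These arguments limit the size of the problem but do not remove it. The photograph rule does not govern the EASI, IGA or tolerability scores. The small head/neck weight gives no protection to the head-region percent change. By barring makeup at the other two scored visits, the protocol itself treats makeup as relevant to assessment.

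A reader might infer that Day 15 is the only on-treatment tolerability score. It is not: one is taken 15 minutes after the first dose, and Day 29 follows dosing through the evening of Day 28. Day 15 is the only mid-treatment one.

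**Conclusion.** This is a minor inconsistency that is worth correcting. The rule as written allows Day 15 to be scored under different conditions from Baseline, which can add measurement error and some apparent improvement to Day 15 secondary results and can hide facial application-site erythema in mid-treatment. A typical size for an affected subject is 2 to 8 percentage points of total EASI at the entry minimum, and more in head-region EASI. The effect on an arm mean cannot be computed from the documents, which give no rate of facial disease, makeup use or masking. The 0.4 to 1.6 points shown above rest on an assumed 10 to 20% of subjects and one or two hidden grades. No size can be put on any effect on TBSA, and I claim none.

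A reader might go further and infer a bias in favour of TER-101 or a flawed primary analysis. The documents support neither. Allocation is 1:1 and both subject and investigator are blinded, so masking should be similar in the two arms and the result is mainly noise and a distorted time course. The primary endpoint compares two makeup-free visits and is reached only indirectly, mainly through subjects without a Day 29 value.

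**What to change.** Extend the makeup sentence in Protocol Section 5.3.1 to the 24 hours before the Baseline, Day 15 and Day 29 visits, so that it matches the emollient rule. Remind subjects at the Day 8 call, which is already scheduled. The cost is a short wording change and one more day without makeup for each subject who wears it; no visit, procedure or analysis is added. If the difference is intended, say so and give the reason in that section.

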5.3.2 Meals and Dietary Restrictions

There are no meal and dietary restrictions for this study other than limiting alcohol usage as follows: no more than 21 drinks/week for males or 14 drinks/week for females (1 drink = 5 ounces [150 mL] of wine or 12 ounces [360 mL] of beer or 1.5 ounces [45 mL] of hard liquor).

5.3.3 Activity

Subjects will be instructed not to bathe, swim, or expose treated areas to water and not to engage in vigorous activity for at least 4 hours after investigational product application.

5.4 Screen Failures

Screen failures are defined as subjects who consent to participate in the clinical study but are not subsequently randomly assigned to study intervention. A minimal set of screen failure information is required to ensure transparent reporting of screen failure subjects to meet the Consolidated Standards of Reporting Trials (CONSORT) publishing requirements and to respond to queries from regulatory authorities. Minimal information includes demography, screen failure details, eligibility criteria, medical history, prior therapies, and any serious AE (SAE).

Individuals who do not meet the criteria for participation in this study (screen failure) may be rescreened once with approval of the study medical monitor. Rescreened subjects should be assigned the same subject number as for the initial screening. Informed consent is required before subjects can be rescreened. See [Section 10.1.3](#) for Informed Consent Process details.

6 STUDY INTERVENTION

Study intervention is defined as any investigational intervention(s), marketed product(s), placebo, or medical device(s) intended to be administered to a study subject according to the study protocol.

[Section 6.3](#) summarizes instructions for preparation, handling, storage and accountability of study interventions. Refer to the IB for more detailed information regarding the storage, preparation, destruction, and administration of each treatment.

6.1 Study Intervention(s) Administered

Intervention Name	TER-101 2.75%	TER-101 Vehicle
Type	Drug	Drug
Dose Formulation	Topical ointment	Topical ointment
Unit Dose Strength(s)	2.75% (w/w)	Not Applicable
Dosing Regimen	Apply a thin film to affected areas twice daily for 28 days	Apply a thin file to affected areas twice daily for 28 days
Route of Administration	Topical application	Topical application
Use	Experimental	Placebo comparator; not distinguishable in appearance from the TER-101 2.75% active ointment
Sourcing	Provided locally by the sponsor/designee	Provided locally by the sponsor/designee
Packaging and Labeling	TER-101 2.75% active ointment will be provided in laminate tubes with a 15 g fill.	TER-101 2.75% ointment vehicle will be provided in laminate tubes with a 15 g fill.
Former Names	ZPL-5212372, PLA-950, WAY-278950, PF-05212372	Not Applicable

6.1.1 Study Treatment Application

TER-101 (2.75% w/w) ointment and ointment vehicle will be applied topically twice a day for 28 days, with at least 8 hours between applications. Subjects will apply sufficient study drug to provide a thin covering. A pea-sized amount (approximately 250 mg) should cover approximately 2% BSA. Additional instructions on application will be provide in the 'Instructions for Use' provided to each subject at randomization.

6.1.2 Excluded Treatments, and/or Procedures During Study Period

Excluded treatments include those that are noted in the exclusion criteria ([Section 5.2](#)) or noted in the washout criteria ([Section 10.9](#)). Subjects should not receive live vaccines during the study or for 30 days after the last dose of investigational product.

6.2 Dose Modification

If a subject develops severe local application site adverse effects or a total skin tolerability score > 7, treatment will be held at that treatment site until the local AE resolves or skin tolerability score returns to baseline. The subject may then reinitiate application of study drug once daily to that site. Any interruptions in study treatment will be recorded, as well as the discontinuation date, restart date, and reason for discontinuation. The reason for discontinuation will also be recorded as an AE (See [Section 8.3](#) for additional information on AEs and SAEs). If the subject continues to experience signs and symptoms of treatment-related AEs, and the discomfort is

intolerable and continues despite decreased frequency of study treatment application, then the study treatment may be discontinued completely, at which time the subject will be discontinued from the treatment period (Day 1 to Day 29). See [Section 7](#) for additional information on discontinuation of study intervention.

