2.3 Benefit/Risk Assessment

TER-101 was safe and well tolerated when administered as a topical ointment (1.0% w/w) twice daily for up to 2 weeks to healthy volunteer subjects (n=8) and patients (n=28) with moderate to severe AD. The most common treatment emergent adverse events (TEAEs) in TER-101 treated subjects were local application site events including pruritus, dry skin, and dermatitis. The majority of reported TEAEs in healthy volunteers or subjects with AD were mild to moderate in

severity. Three of 10 subjects with moderate to severe AD randomized to the vehicle arm withdrew due to TEAEs related to lack of efficacy. No healthy volunteers or subjects with AD treated with TER-101 withdrew from the study. There were no clinically significant safety concerns identified in vital signs, physical examinations, electrocardiograms (ECGs), or clinical laboratory assessments.

In this small study, there was no statistically significant difference in the primary efficacy analysis (percentage change from baseline in Eczema Area and Severity Index [EASI] score at Week 2) or in a sensitivity analysis using multiple imputation, between the TER-101 and placebo groups. In the sensitivity analysis using last observation carried forward, there was evidence of a trend towards a larger decrease in EASI scores and other efficacy assessments in the TER-101 compared with the placebo group. This result was also supported by the worst-case imputation sensitivity analysis. Three patients in the TER-101 group were assessed as EASI-75 (75% reduction in EASI score from baseline) responders. No patients in the placebo group met this definition. A trend towards greater improvement in the TER-101 group was also evident in the Patient Global Impression of Change assessment.

Teres Bio anticipates the most likely TEAE in the Phase 2 upcoming study will be local application site TEAEs including pruritus, dry skin, stinging/burning, pain, or dermatitis including atopic dermatitis. The protocol includes rules for treatment cessation in the event that subjects develop severe local TEAEs or high scores on the tolerability assessments. Once local AEs have abated, treatment may be re-initiated once daily. Teres Bio believes that the accrued clinical safety and preliminary efficacy data support a favorable benefit-risk profile for the proposed protocol and that appropriate monitoring and stopping rules have been included in the planned study design.

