9.4.4 Safety Endpoints

- Safety: TEAEs, SAEs, change from baseline in vital signs, ECGs, and laboratory assessments
- Tolerability: Scored by investigator at baseline, post-baseline visits on 4-point scale (0 = none; 3 = severe) to include subscores for erythema, burning/stinging, pruritus.

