10.3.3 Recording and Follow-Up of Adverse Events and/or Serious Adverse Events

AE and SAE Recording

- When an AE/SAE occurs, it is the responsibility of the investigator to review all documentation (eg, hospital progress notes, laboratory reports, and diagnostics reports) related to the event.
- The investigator will then record all relevant AE/SAE information in the electronic case report form (eCRF).
- It is **not** acceptable for the investigator to send photocopies of the subject's medical records in lieu of completion of the AE/SAE eCRF page.
- There may be instances when copies of medical records for certain cases are requested by sponsor. In this case, all subject identifiers, with the exception of the subject number, will be redacted on the copies of the medical records before submission to sponsor.
- The investigator will attempt to establish a diagnosis of the event based on signs, symptoms, and/or other clinical information. Whenever possible, the diagnosis (not the individual signs/symptoms) will be documented as the AE/SAE.
- The investigator must assign the following AE attributes:
 - AE diagnosis or syndrome(s), if known (if not known, signs or symptoms).
 - Dates of onset and resolution (if resolved).
 - Intensity (or toxicity defined below).
 - Assessment of relatedness to investigational product, other protocol-required therapies; and
 - Action taken.

Assessment of Intensity

The investigator will make an assessment of intensity for each AE and SAE reported during the study and assign it to 1 of the following categories:

- Mild: An event that is easily tolerated by the subject, causing minimal discomfort and not interfering with everyday activities.
- Moderate: An event that causes sufficient discomfort and interferes with normal everyday activities.
- Severe: An event that prevents normal everyday activities. An AE that is assessed as severe should not be confused with a SAE. Severe is a category utilized for rating the intensity of an event; and both AEs and SAEs can be assessed as severe.

An event is defined as ‘serious’ when it meets at least 1 of the predefined outcomes as described in the definition of an SAE, NOT when it is rated as severe.

Assessment of Causality

- The investigator is obligated to assess the relationship between study intervention and each occurrence of each AE/SAE. The AEs must be characterized as related or unrelated. See [Section 10.4](#) for a two-level definition of causality rating.

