10.7 Appendix 7: Local Tolerability

The investigator will assess local tolerability by inspecting the application sites for application site erythema and query the subject as to symptoms of burning/stinging or pruritus associated with study drug application. The local tolerability assessment will be conducted at baseline pre-dose and approximately 15 minutes after the first dose, Day 15, and Day 29. The investigator should score the in individual components of burning/stinging, pruritus, and erythema based on the average for score of all application sites.

Grade	Burning/Stinging	Pruritus	Erythema
0 (none)	No stinging/burning	No pruritus	No detectable erythema, skin of normal color
1 (mild)	Slight warm, tingling sensation, not really bothersome	Occasional, slight itching/scratching	Skin pinkness present
2 (moderate)	Definite warm, tingling sensation that is somewhat bothersome	Constant or intermittent itching/scratching which is not disturbing sleep	Definite redness, easily recognized
3 (severe)	Hot, tingling/stinging sensation	Bothersome	Intense redness

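### The Synopsis and Section 6.2 give different tolerability-score triggers for the same local treatment hold; on whole grades 3+3+0 and 3+3+1 meet only the Synopsis rule

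*Protocol*

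**What the plan says.** Protocol Section 6.2 (Dose Modification) holds treatment for severe local application site effects or on the score: "a total skin tolerability score > 7, treatment will be held at that treatment site". After resolution or return to the baseline score, "The subject may then reinitiate application of study drug once daily to that site".

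The Synopsis (Section 1.1) describes the same action. It also starts with severe local application site AEs, but its score trigger reads "scores of 3 on two or more tolerability subscores arise with BID dosing, treatment will be withheld to the affected area". The release condition matches, and "subjects may restart application to the affected area once daily". The paragraph closes with a pointer to Section 6.2.

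The scale is described in Section 9.4.4: "post-baseline visits on 4-point scale (0 = none; 3 = severe) to include subscores for erythema, burning/stinging, pruritus". Appendix 7 (Section 10.7) tabulates grades 0, 1, 2 and 3 and sets the components of burning/stinging, "pruritus, and erythema based on the average for score of all application sites". It gives no rounding rule. SAP Section 3.7.2 tabulates grades 0 to 3 only. The SAP does not state or reconcile the two triggers.

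The benefit-risk argument in Section 2.3 relies on these rules: "The protocol includes rules for treatment cessation in the event that subjects develop severe local TEAEs or high scores on the tolerability assessments".

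**The concern.** These are two versions of one safety rule, and they set different thresholds. A site working from the Synopsis and a site working from Section 6.2 could treat two subjects with the same scores differently.

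Three things depend on the choice:

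- whether a subject with two grade-3 subscores and a low third one keeps applying ointment twice daily to the area;
- whether a hold-related AE exists at all, because Section 6.2 requires the reason for a hold to be recorded as an AE, and this feeds the SAP 3.7.3 summaries of TEAEs leading to interruption;
- whether missed doses are excused, because Section 8.3.5 exempts holds made under Section 6.2 from the noncompliance pathway and does not mention the Synopsis rule.

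**Working it through.** The documents give no derivation of the cut-off of 7, so there is no figure to reproduce. The check is a comparison of the two rules.

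**Inputs.** Three subscores (Section 9.4.4), each graded 0 to 3 (Section 8.3.4, Appendix 7). Maximum total = 3 × 3 = 9. Whole-grade patterns = 4³ = 64.

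**Whole grades.**

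- Synopsis rule (at least two 3s): 3 positions for the odd score × 3 lower grades, plus 3+3+3, = 10 patterns.
- Section 6.2 score rule (total of 8 or 9): three orderings of 3+3+2, plus 3+3+3, = 4 patterns.
- All 4 lie within the 10, so 10 − 4 = 6 differ: three orderings of 3+3+0 (total 6) and three of 3+3+1 (total 7).

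**Could another cut-off on the total reproduce the Synopsis rule?** No.

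| Total | Synopsis patterns missed | Other patterns added |
|---|---|---|
| > 5 | 0 | 10 |
| > 6 | 3 | 3 |
| > 7 | 6 | 0 |
| > 8 | 9 | 0 |

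**If averaging over sites gave half grades** (an assumption; the table lists whole grades only). Patterns = 7³ = 343. Synopsis rule: 3 × 6 + 1 = 19. Total above 7: 20. Both: 10. Synopsis only: 19 − 10 = 9. Section 6.2 only: 20 − 10 = 10, for example 2.5+2.5+2.5 = 7.5. The mismatch then runs in both directions.

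**When a score can lead to a hold.** Scores are taken pre-dose and 15 minutes after the first dose on Day 1, and on Days 15 and 29. Dosing ends with the evening dose on Day 28. On the nominal schedule that leaves the 15-minute and Day 15 scores.

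**Exposure after an added hold.** From day d through Day 28 there are 2 × (28 − d + 1) applications, and once-daily dosing gives at most half:

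- Day 15: 28 become at most 14. Visit window limits: Day 12, 34 become 17; Day 18, 22 become 11. This assumes no dose that morning before the visit; with one on Day 15, 27 remain and at most 13 are given.
- After the first dose on Day 1: 56 − 1 = 55 remain, and once daily from Day 2 gives at most 27.

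All of these are upper limits, because they assume immediate release of the hold.

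**The case against.** The strongest reply is that the other trigger closes the gap. Section 6.2 also holds for severe local effects, grade 3 is labelled severe on the tolerability scale, and raters are told to separate tolerability findings from the underlying AD. On that reading, two grade-3 subscores already are severe local effects.

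This may be how some investigators would act, but the text does not make it so. The protocol defines AE intensity separately: "Severe: An event that prevents normal everyday activities". Grade 3 in Appendix 7 does not require that. If any grade 3 counted as severe, 64 − 27 = 37 of 64 patterns would trigger a hold, including every pattern either score rule catches, and neither score rule could ever add a case. Section 2.3 lists severe events and high scores as alternatives, which suggests that the score is meant to add something. That is an inference from one summary sentence, not a statement of the rule.

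The second reply is that Section 6.2 is the operative section and the Synopsis refers to it. This carries weight, and Section 8.3.5 points the same way. But no text states precedence, and the Synopsis still gives sites a different instruction.

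The third reply concerns the remedy and stands. A reader might infer that the Synopsis rule is always the more protective and should simply replace the cut-off of 7. The documents do not support that. With subscores averaged over sites and no rounding rule, 2.5+2.5+2.5 would be held only under Section 6.2, so plain replacement could remove protection.

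**Conclusion.** The inconsistency is real and minor. On whole grades, which the scale table and the SAP tabulation show, 3+3+0 and 3+3+1 trigger a hold under the Synopsis and not under the Section 6.2 score rule. The severe-event trigger may cover some of these subjects, but not by definition.

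The pattern counts describe the rules, not patients. The documents give no distribution of scores, so the number of subjects affected is unknown and may be zero.

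Two stronger readings should be resisted. A reader might infer that subjects with two grade-3 subscores would go unprotected under Section 6.2; the severe-event trigger remains available to the investigator. A reader might also infer either that the primary result is compromised or that it cannot be touched. Neither follows. The primary analysis method is unchanged by the choice of trigger, but an added hold followed by once-daily dosing reduces exposure at that area and could affect that subject's Day 29 EASI.

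**What to change.** State one identical trigger in the Synopsis and in Section 6.2. Hold treatment to the area for any of:

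- a severe local application site AE, with intensity as defined in Section 10.3.3;
- a score of 3 on two or more subscores;
- a total above 7.

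On whole grades this equals the Synopsis rule, because every total above 7 already contains two 3s. If averaging gives fractional scores, it keeps every score-based hold that either text now gives (on the half-grade assumption, 19 + 20 − 10 = 29 of 343 patterns). Naming the intensity definition also settles which meaning of severe applies.

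The cost is a clarifying amendment and a site memo, with no new visit, assessment or subject. The downside is possibly a few more temporary holds, some reflecting AD itself (for instance erythema 3 and pruritus 3 without burning), so sites need reminding of the Section 8.3.4 instruction to distinguish the two. Each added hold carries the exposure loss shown above. The next scheduled score is 14 days away (Day 15 after a Day 1 hold, Day 29 after a Day 15 hold). After a Day 1 hold, the Day 8 contact offers a scheduled point to judge whether the AE has resolved. After a Day 15 hold, an earlier restart needs an unscheduled check or a judgement that the AE has resolved.
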